5.3 Analysis Populations

5.3.1 *Safety Population*

The safety population (SP) is defined as the population of subjects who had any treatment attempted or completed. The safety population will be used in analysis of all safety endpoints including the primary endpoint.

5.3.2 *Intent-to-Treat Population*

The ITT population is defined as all subjects enrolled, excluding screen failures.

5.3.3 *Modified Intent-to-Treat Population*

Analysis of the efficacy endpoints will use the modified Intent-to-Treat (mITT) population as a primary efficacy analysis population. The mITT population is defined as all subjects who successfully received treatment but excluding:

- subjects in whom treatment was attempted but not completed and;
- subjects who discontinue from the study prior to evaluation of treatment failure/success for the 8-week efficacy endpoint if the reason for exit is not related to CDI symptoms. Reason for exit will be

captured on the exit form to allow for identification of such subjects. Examples of reasons unrelated to CDI symptoms may include:

- Withdrawal of consent
- Death unrelated to CDI

5.3.4 *Per-Protocol Population*

The per-protocol (PP) population will consist of all subjects who successfully received treatment analyzed according to the treatment they received, excluding:

- Subjects who have documented protocol deviations to inclusion or exclusion criteria.
- Subjects who exited prior to the 8-week efficacy evaluation if the reason for exit was not related to CDI symptoms in the same manner as the mITT population.

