6.7.1.1.1 Recurrence of CDI within 8 weeks of treatment

Recurrence of CDI is defined as the presence of CDI diarrhea within 8 weeks (54-60 days) of administration of a study enema, which includes a positive stool test for *C. difficile* as determined by the central laboratory. A CDI with an onset after 8 weeks (> 60 days) from completion of the study treatment is considered a new CDI. Onset of CDI is the date that the symptoms first started.

The efficacy parameter used to determine treatment success is defined as the absence of CDI diarrhea through 8 weeks after completing a study treatment. Efficacy assessments will occur at each scheduled contact: 1-week, 4-weeks, 8-weeks.

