6.7.1.2 Sensitivity Analysis for the Efficacy Endpoints

The efficacy analyses will be repeated using the ITT and PP population to assess the sensitivity of the endpoints. The ITT analysis will serve as the conservative analysis as it considers all subjects who exit prior to the 8-week efficacy assessment as treatment failures regardless of treatment failure documentation.

Finally, the sensitivity of the efficacy endpoints will be assessed in a multivariate logistic regression adjusting for possible interactions of the following covariates: age (< 65 years, ≥ 65 years), sex (Female, Male), race group (White, Non-white), ethnicity (Hispanic-Latino, not Hispanic-Latino), site geography (outside the US, Eastern US*, Southern US*, Northern US*, Western US*), and categories of number of previous episodes of CDI recurrence at Baseline (≤ 3 , > 3). Comorbidities will also be reviewed for possible interactions. This analysis will be performed on all populations where at least 20 subjects are available in each sub-group.

*States included in the identified US geographical regions are as follows:

- Eastern US: Connecticut, Delaware, District of Columbia, Maine, Maryland, Massachusetts, New Hampshire, New Jersey, New York, Ohio, Pennsylvania, Rhode Island, Vermont, Virginia, West Virginia
- Southern US: Alabama, Arkansas, Georgia, Florida, Kansas, Kentucky, Louisiana, Mississippi, North Carolina, Oklahoma, South Carolina, Tennessee, Texas
- Northern US: Illinois, Indiana, Iowa, Michigan, Minnesota, Missouri, Nebraska, North Dakota, South Dakota, Wisconsin
- Western US: Arizona, California, Colorado, Idaho, Montana, Nevada, New Mexico, Oregon, Utah, Washington, Wyoming

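### On the natural reading, mITT and PP drop event-free early exits but keep failures determined before exit, and ITT scores every exit as a failure; if exits are non-informative, mITT overstates 8-week recurrence slightly and ITT more, and no planned analysis uses the partial follow-up

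*SAP*

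**What the plan says.** SAP 5.3.3 makes mITT the primary efficacy population. From subjects who received a complete enema it removes "subjects who discontinue from the study prior to evaluation of treatment failure/success for the 8-week efficacy endpoint", but only where the exit has a cause other than CDI. Exits for CDI-related reasons therefore stay in. SAP 5.3.4 removes from PP "Subjects who exited prior to the 8-week efficacy evaluation if the reason for exit was not related to CDI symptoms" and ties this to the mITT rule.

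SAP 6.7.1.2 repeats the efficacy analyses in ITT and PP. It states that "The ITT analysis will serve as the conservative analysis", because "it considers all subjects who exit prior to the 8-week efficacy assessment as treatment failures regardless of treatment failure documentation". The denominator is wider than the treated set: "The ITT population is defined as all subjects enrolled, excluding screen failures" (SAP 5.3.2).

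SAP 6.7.1.1.1 dates a recurrence: "Onset of CDI is the date that the symptoms first started". The same section treats a CDI with onset after day 60 as a new infection. No time-to-event analysis is listed. SAP 7.3 rules out imputation except for the Cdiff32 scores.

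**The concern.** The two outcomes are not determined on the same clock. Failure can be established on any day up to week 8, at an unscheduled visit with a central stool test (Protocol 7.3.6, 10.13). Success needs the full 8 weeks without CDI diarrhea and is assessed at the 8-week visit (Protocol 7.3.7, 10.11). A subject who fails at week 3 and then withdraws has been evaluated before exit. A subject who withdraws event-free at week 5 cannot have been. On the natural reading of SAP 5.3.3 the first is kept and the second dropped, so membership of the main analysis set depends partly on the outcome.

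ITT puts the event-free exits back, but as failures. Under non-informative exit both estimates then lie on the same side of the true rate. In a single-arm study the absolute rate is the efficacy result, and there is no second arm against which such a shift could cancel.

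**Working it through.** **No plan figure to reproduce.** The SAP states no expected recurrence rate or dropout rate, and no power (SAP 3.3). The inputs below are proxies from the sponsor's earlier studies, assumed for this trial.

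**Inputs**
- True 8-week recurrence F: 1 − 0.789 = 21.1% (study 2015-01, Protocol 5.3.3) and 1 − 0.704 = 29.6% (study 2017-01, Protocol 5.3.4).
- Share d with an exit time before week 8: 5/267 = 1.9% (262 of 267 with an adjudicated outcome, Protocol 5.3.4); 7/149 = 4.7% (142 of 149 evaluable, Protocol 5.3.3); 3/34 = 8.8% (31 of 34 with efficacy data, Protocol 5.3.1).
- Assumed timing: exits uniform over 8 weeks and independent of recurrence. Recurrence is either uniform or front-loaded (exponential truncated at 8 weeks, with rate 3 per 8-week period).
- a = mean probability of having recurred by the exit time: F/2 if uniform, 0.719F if front-loaded.

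**Formulas**
- mITT, with failures before exit kept and event-free exits dropped: [(1−d)F + d·a] / [(1−d) + d·a]. The bias is d·a(1−F) / [(1−d) + d·a], which is never negative.
- ITT among treated subjects: F + d(1−F).

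**Worked case:** F = 29.6%, d = 4.7%, uniform timing, a = 0.148.
- mITT = (0.953 × 0.296 + 0.047 × 0.148) / (0.953 + 0.047 × 0.148) = 0.2890/0.9600 = 30.1%.
- ITT = 0.296 + 0.047 × 0.704 = 32.9%.

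**All cases** (ranges run from uniform to front-loaded; shifts in percentage points)

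| F | d | mITT shift | ITT shift |
|---|---|---|---|
| 21.1% | 1.9% | 0.16–0.23 | 1.50 |
| 21.1% | 4.7% | 0.41–0.59 | 3.71 |
| 21.1% | 8.8% | 0.80–1.14 | 6.94 |
| 29.6% | 1.9% | 0.20–0.29 | 1.34 |
| 29.6% | 4.7% | 0.51–0.73 | 3.31 |
| 29.6% | 8.8% | 0.99–1.42 | 6.20 |

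The 95% half-width at n = 750 is 1.96 × √(F(1−F)/750), which is 2.9 points at 21.1% and 3.3 points at 29.6%.

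**Two things the table leaves out**
- The proxies are shares without an outcome, which is closer to d(1−a) than to d. Converting the extreme case (F = 29.6%, front-loaded, a = 0.213) gives d = 0.088/0.787 = 11.2%. The mITT shift becomes 0.112 × 0.213 × 0.704 / 0.912 = 1.8 points. The largest ITT shift (F = 21.1%, a = 0.152) becomes (0.088/0.848) × 0.789 = 8.2 points. The picture does not change.
- The SAP's ITT set can also contain consented, eligible subjects who left before dosing. Scoring them as failures would raise ITT further.

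**Simulation** (4,000 runs, n = 750, F = 29.6%, uniform timing). At d = 4.7%: Kaplan-Meier 29.6%, mITT 30.1%, ITT 32.9%, with about 30 event-free exits. The run-to-run standard deviation is 1.69 points for Kaplan-Meier and 1.70 for mITT, so there is no loss of precision. At d = 15%, a stress case above every proxy: 29.6%, 31.4% and 40.1%.

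**When the mITT direction changes**
- The true rate is a weighted mean of the mITT rate and the later recurrence risk q of the dropped subjects, so mITT understates once q exceeds the mITT rate. Under independence the residual risk is (F−a)/(1−a). At F = 29.6% and d = 4.7% that is 17.4% (uniform) or 10.6% (front-loaded), against break-even values of 30.1% and 30.3%: ratios of 1.7 and 2.9. At F = 21.1% the ratios are 1.8 and 3.1.
- If subjects who failed and then exited were also dropped, only those without an early exit would remain. Under independence their rate is F, so the bias is zero.

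**The case against.** The strongest reply has four parts.

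1. A reader might infer that mITT and ITT both certainly overstate recurrence. The documents do not support that for mITT. The SAP never says that a failure determined before exit is retained, and the PP wording can be read to drop such a subject. Nor do the documents establish that exits are unrelated to later recurrence. Withdrawal of consent is listed as an example of a non-CDI reason, and failure needs a central-laboratory positive. A subject who withdraws with an untested recurrence disappears from mITT and pulls its rate down. This stands, so the mITT direction is conditional.
2. The mITT shift is below sampling error at every document-based exit share. This stands too.
3. The ITT rule is deliberate. The SAP names it conservative and says what it does with exits; it does not claim that mITT and ITT bracket the truth. There is no concealment, but the size of the shift is not shown, and nothing planned separates the scoring rule's contribution from real failures.
4. The endpoint is secondary and descriptive, with no success threshold; under non-informative exit the shift works against the product; and SAP 6.1 already identifies treated subjects who withdraw before the 8-week evaluation, with reasons. That lowers the stakes. It does not supply an estimate that uses their follow-up.

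Kaplan-Meier itself assumes non-informative exit, so it does not answer the untested-recurrence worry. It removes the selection and scoring effects, not informative dropout.

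**Conclusion.** The point holds in conditional form. Given non-informative exit and retention of failures determined before exit, mITT overstates 8-week recurrence by about 0.2 to 1.4 points and ITT by about 1.3 to 6.9 points at the proxy exit shares, so the two do not bracket the true rate. The ITT shift is the material one: at 4.7% exits it already slightly exceeds the 95% half-width, and at 8.8% it is about twice that. The mITT shift is minor, can reverse under informative exit, and is zero under independence if failed-then-exited subjects are also removed. Whatever the direction, no listed analysis uses the event-free time of subjects who leave early. This is a worthwhile, inexpensive improvement; it does not make the planned results uninterpretable. The sizes rest on earlier studies' rates and on assumed timing, since this plan gives neither.

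**What to change.** In SAP 6.7.1.2, add a Kaplan-Meier estimate of 8-week recurrence with a 95% CI in all subjects with a completed enema, specified as follows:

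- Time the event by symptom-onset date and fix one horizon consistent with SAP 6.7.1.1.1, for example day 60.
- State that a failure determined before exit always counts, and word 5.3.3 and 5.3.4 to match.
- Censor event-free non-CDI exits at last contact.
- Score CDI-related exits without a confirmed failure as failures in one run and as censored in another.
- Add a cumulative-incidence check with non-CDI death as a competing event.
- Report the estimate beside mITT and ITT, and describe ITT as an upper bound with respect to exits. State how Indeterminate outcomes (SAP 3.1.4) are scored, since that description depends on it.

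The dates are already collected: symptom start (Protocol 10.13), exit date (10.15) and last actual encounter for loss to follow-up (10.16). The cost is one extra analysis and a few sentences. Its downside is the assumption of non-informative exit, which should be stated with the result.

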5.4 Safety Variables

Assessment of the primary safety objective and other safety objectives will be performed on all subjects exposed to RBX2660 (Safety Population, see Section 6.3.1), and will include descriptive statistics. Additional sub-analyses of safety data may be performed on sub-populations.

5.4.1 *Primary Safety Endpoint*

Number of subjects with investigational product- and/or enema-related treatment-emergent adverse events (TEAEs).

5.4.2 *Other Safety Endpoints*

1. Number of adverse events per subject
2. Timing of attributable TEAEs
3. Duration of TEAEs
4. Relatedness of TEAEs
5. Severity of TEAEs
6. Causality of TEAEs to IP, enema, *C. difficile* or prior condition
7. Number of each of the following CDI-related TEAEs through 8-weeks post treatment: death, septic shock, toxic megacolon, colonic perforation, emergency colectomy, and intensive care unit (ICU) admission
8. Onset of new chronic conditions relative to treatment administration

5.4.3 *Adverse Events*

An adverse event (AE) is any untoward medical occurrence associated with the use of IP, whether or not the event is considered product-related. Preexisting conditions that worsen in frequency, intensity or character of the condition during study participation will be recorded as an AE. AEs will be recorded for each subject from the day of enrollment through the 6-month telephone assessment. Serious adverse events (SAEs) will be recorded for each subject from the day of enrollment through the duration of the study.

5.4.3.1 Adverse Event Dictionary

AEs and SAEs will be classified by the Medical Dictionary for Regulatory Activities (MedDRA) version 20.0. The verbatim term recorded by the investigator will be mapped in MedDRA and system organ class (SOC), high level group term (HLGT), high level term (HLT), preferred term (PT), and lower level term (LLT) will be attached to the clinical database. Tables and listings will present data at the SOC and PT level.

5.4.3.2 Adverse Event Severity

Severity of AEs will be graded as mild, moderate, severe, or potentially life-threatening. The severity grade of events for which the investigator did not record severity will be categorized as “Unknown” for tabular summaries and data listings and will be considered the least severe for the purposes of sorting for data presentation. For summaries by severity grade, if a subject has multiple events occurring in the same SOC or PT, then the most severe event will be selected.

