11.7. Grading Event Severity

Identified, subject-reported and unsolicited AEs are to be graded, according to severity, by the site investigator. For this classification of events, severity is not the same as

seriousness, which is defined in **Section 11.1**. Severity is an indication of the *intensity* of a specific event (e.g., mild, moderate or severe). Classification of an event as serious relates to an event's outcome or intervention criteria and is usually associated with events that pose a threat to a subject's life or functioning. An event can be severe but not serious, such as a migraine.

Using the definitions in **Table 11-1**, the site investigator will categorize the severity of a solicited or unsolicited event on the AE eCRF. If a particular event is not listed on this table, the NIH/NCI Common Terminology Criteria for Adverse Events found at online at the following address may be utilized.

https://ctep.cancer.gov/protocolDevelopment/electronic_applications/docs/CTCAE_v5_Quick_Reference_8.5x11.pdf

Table 11-1: Severity Grading Table*

Parameter	Grade 1: Mild	Grade 2: Moderate	Grade 3: Severe	Grade 4: Potentially Life-threatening
Flatulence (gas)	Symptoms causing no or minimal interference with usual social and functional activities	Symptoms causing greater than minimal interference with usual social and functional activities	NA	NA
Belching (burping)	Symptoms causing no or minimal interference with usual social and functional activities	Symptoms causing greater than minimal interference with usual social and functional activities	NA	NA
Abdominal distension or bloating	Symptoms causing no or minimal interference with usual social and functional activities	Symptoms causing greater than minimal interference with usual social and functional activities	Symptoms causing inability to perform usual social and functional activities	NA
Increased diarrhea	Increase of ≤ 3 stools over baseline per 24-hour period	Increase of 4 – 6 stools over baseline per 24-hour period	Bloody diarrhea if not present at baseline OR increase of ≥ 7 stools over baseline per 24-hour period OR IV fluid replacement indicated if not indicated at baseline	Life-threatening consequences, e.g., hypotensive shock

Parameter	Grade 1: Mild	Grade 2: Moderate	Grade 3: Severe	Grade 4: Potentially Life-threatening

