- Serious TEAEs by relatedness to *C. difficile* disease
- Serious TEAEs by relatedness to enema procedure
- Serious TEAEs by relatedness to preexisting condition
- Serious TEAEs resulting in subject withdrawal
- Serious TEAEs resulting in death

For the summary of AEs by maximum severity, if a subject has multiple events occurring in the same SOC or same PT, then the event with the highest severity will be counted. For AEs reported by causality, if a subject has multiple events occurring in the same SOC or same PT, the event with the highest association will be summarized.

A summary of TEAE and serious TEAE characteristics (severity, relatedness to IP, relatedness to *C. difficile* disease, relatedness to enema procedure, and relatedness to preexisting condition by outcome) will also be presented by first and second enema and overall.

Incidence of AEs and serious AEs will also be presented by onset interval separately for the first and second enemas (as applicable), as well as a combined presentation for the following intervals:

- Baseline (onset date prior to date of first enema)
- IP administration (onset date on the date of the first and second enema, as applicable)
- Intervals relative to the enema date (first and second enemas, as applicable):
 - 1-Week (day 8), 4-Weeks (day 29), 8-Weeks (day 57), 4 Months (Day 120), and 6 Months (Day 180).

For data presentation, SOC will be ordered alphabetically, with PT sorted by decreasing total frequency. No inferential statistics will be provided for the AE data.

Subject listings will be presented for all AEs including SAEs.

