7.3 Handling of Dropouts or Missing Data

No imputations will be used in analyses/summaries. However, a LOCF analysis will be used for evaluation of the Cdiff32 scores. Missing safety data will not be imputed beyond the adjustments for adverse event data mentioned in **Section 6.4.3**.

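### Ungraded adverse events rank lowest when the worst event per subject is picked, so the maximum-severity tables can understate, but never overstate, severe TEAEs (minor)

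*SAP*

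**What the plan says.** SAP 5.4.3.2 grades events as mild, moderate, severe or potentially life-threatening. On missing grades it says: "The severity grade of events for which the investigator did not record severity will be categorized as" 'Unknown', in tables and listings, and that such an event "will be considered the least severe for the purposes of sorting for data presentation". The next sentence sets the selection rule for severity summaries: "if a subject has multiple events occurring in the same SOC or PT, then the most severe event will be selected". SAP 6.6.2.1 repeats it for the maximum-severity tables: "if a subject has multiple events occurring in the same SOC or same PT, then the event with the highest severity will be counted".

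SAP 7.3 closes off other handling: "Missing safety data will not be imputed beyond the adjustments for adverse event data mentioned in" the adverse event section. (It cites 6.4.3, which does not exist in the SAP. The adverse event rules stand in 5.4.3.) No sensitivity table for missing severity is planned.

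Two provisions limit the problem. Protocol 11.7 says that "the site investigator will categorize the severity of a solicited or unsolicited event on the AE eCRF", and SAP 6.6.2.1 says "Subject listings will be presented for all AEs including SAEs".

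**The concern.** Picking a maximum requires an order, and 5.4.3.2 supplies the only order that includes 'Unknown'. A programmer would naturally use it. A subject with one mild and one ungraded event in the same SOC is then tabulated as mild, and nothing in that table shows that a second event had no grade.

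This is the one missing-data rule of its kind that leans in the favourable direction. Under SAP 5.4.3.4, an event with a partial onset date in the month or year of the first enema counts as treatment-emergent. Under SAP 6.7.1.2, the ITT analysis counts subjects who exit before the 8-week assessment as failures and describes itself as conservative. Safety is the primary objective, severity of TEAEs is a named safety endpoint (SAP 5.4.2), and two tables depend on the rule: TEAEs by maximum severity and serious TEAEs by maximum severity.

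**Working it through.** The plan states no figure on this point, so there is none to reproduce. The check applies the rule and then sizes it.

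**1. What the rule does.** Take the order Unknown < Mild < Moderate < Severe < Potentially life-threatening and the maximum within a subject and a SOC or PT:

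| Events in the cell | Tabulated as |
|---|---|
| Unknown + Unknown | Unknown |
| Unknown + Mild | Mild |
| Unknown + Moderate | Moderate |
| Unknown + Severe | Severe |
| Unknown + Potentially life-threatening | Potentially life-threatening |

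Across all 5 × 5 × 5 = 125 ordered three-event combinations, no cell with a recorded severe or worse event is tabulated below severe. The tabulated grade is wrong only when the ungraded event was truly worse than the highest recorded one. The severe-or-worse count can thus be too low but not too high.

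**2. Effect on the severe-or-worse count.** Inputs:
- 750 treated (Protocol 12.1).
- 178 of 267 subjects with a TEAE in the earlier Phase 3 study (Protocol 5.3.4), so 750 × 178/267 = 500 subjects.
- 46 severe and 5 potentially life-threatening of 368 entries in that study's maximum-severity split, so 51/368 = 13.9%. This is a share of entries; applying it to subjects is an assumption.
- Ungraded share q: not in the documents; assumed 1%, 2% and 5%, missing at random.

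With one event per subject, the true count is 500 × 51/368 = 69.3. The tabulated count is 69.3 × (1 − q). If every ungraded event is counted as severe, it is 69.3 × (1 − q) + 500q.

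| q | Tabulated | Shortfall (points of 750) | Ungraded counted as severe | Above tabulated (points of 750) |
|---|---|---|---|---|
| 0% | 69.3 | 0 | 69.3 | 0 |
| 1% | 68.6 | 0.7 (0.09) | 73.6 | 5 (0.67) |
| 2% | 67.9 | 1.4 (0.18) | 77.9 | 10 (1.33) |
| 5% | 65.8 | 3.5 (0.46) | 90.8 | 25 (3.33) |

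In this one-event case the ungraded subjects appear in the 'Unknown' row. Concealment needs a graded event in the same cell, which is step 3.

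**3. How many subjects could have an ungraded event that the table does not show.** The earlier study had 708/178 = 3.98 TEAEs per subject with any. Let events per subject be 1 + Poisson(λ), with λ = 2.98, and take all of a subject's events as one cell. The chance of at least one ungraded and at least one graded event is [1 − (1 − q)e^(−λq)] − q·e^(−λ(1−q)). For 500 subjects:
- q = 1%: 19.5 − 0.3 = about 19
- q = 2%: 38.3 − 0.5 = about 38
- q = 5%: 90.7 − 1.5 = about 89

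These figures do not depend on the severity split. They are on the high side for any one cell, because the SAP selects within SOC or PT, where fewer events meet. They also count subjects with an ungraded event of any true grade, so most have no wrong grade.

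**4. Why 'Unknown' should not simply be ranked higher.** Placing it above severe turns Unknown + Severe into Unknown. A simulation with the event counts of step 3 and per-event grades of 43.05% mild, 43.05% moderate, 12.5% severe and 1.4% potentially life-threatening shows the cost. About 7, 13 and 31 of 500 subjects with a recorded severe maximum would leave the severe row at q = 1%, 2% and 5%. The SAP's rule loses about 2, 3 and 8 true severe-or-worse subjects. The even split of mild and moderate is assumed. The model reuses maximum-severity shares as per-event shares and so puts about 215 of 500 subjects at severe or worse; only the comparison between the two rules is useful, not the levels.

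**The case against.** The strongest case on the other side has four parts.

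First, the lowest rank is worded for sorting in data presentation, and the SAP never says that it governs selection. That stands as a point of wording: its use in selection is an inference. But no other rule places 'Unknown', so the ambiguity is itself a reason to settle it.

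Second, reporting the highest recorded grade is not favourable imputation; it reports what was recorded, in line with SAP 7.3, and the data are descriptive. This stands, and it is why the main table should stay as it is.

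Third, safeguards exist. Investigators are to grade events, and ungraded events stay visible in the listings and perhaps in the summary of TEAE characteristics in SAP 6.6.2.1. Serious TEAEs, deaths and withdrawals are also tabulated without regard to grade. This mostly stands, but none of these shows how many subjects in the maximum-severity tables are affected.

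Fourth, grades may hardly ever be missing. The earlier Phase 3 split adds up exactly (317 + 46 + 5 = 368) and leaves no ungraded entry. That stands too: the effect may be nil.

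A reader might infer that the tables will understate severe TEAEs, or that subjects with ungraded events are reported at a lower grade. The documents do not support either as a general statement. Understatement requires an ungraded event that was truly severe, and a subject with only ungraded events in a cell is shown as 'Unknown'.

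**Conclusion.** The point holds as a minor one. As written, the SAP lets an ungraded event disappear behind a lower recorded grade in the same SOC or PT, and any resulting error in the severe-or-worse count is downward. The plan offers no bound on that error.

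The size depends wholly on the ungraded rate, which the documents do not give. It is zero with complete grading. With about 500 subjects having a TEAE, the one-event illustration puts it at 0.7 subjects at 1% ungraded and 3.5 at 5%, missing at random. It would be larger if severe events were more often left ungraded; counting every ungraded event as severe gives 73.6 and 90.8 subjects, against 68.6 and 65.8 tabulated. These figures borrow the earlier study's rates and are illustrations, not predictions.

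The primary endpoint, the number of subjects with product- or enema-related TEAEs, is unaffected.

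**What to change.** In SAP 5.4.3.2 and 6.6.2.1:

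- State that the main maximum-severity tables show the highest recorded grade, and 'Unknown' only where a subject has no graded event in that SOC or PT.
- Add a sensitivity version of TEAEs by maximum severity and of serious TEAEs by maximum severity. In it, count each ungraded event as severe, without displacing any recorded severe or potentially life-threatening event.
- Footnote the main tables with the number of ungraded events and the number of subjects whose tabulated grade excludes one.
- Do not rank 'Unknown' above recorded severe events.

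The cost is a few sentences, two extra tables from the same program with a changed sort key, and a footnote. The sensitivity count is an upper bound on severe or worse, so it will look less favourable and may overstate. If no grades are missing at database lock, the footnote says so and the extra tables match the main ones.
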